6.4 STUDY INTERVENTION COMPLIANCE

Subjects will be closely monitored during each treatment session to ensure appropriate dosing of the phototherapy device (as determined by length of treatment time) and subject's adherence to the protocol (i.e., the subject remains with both treatment and mock-treatment devices in the correct position). The exact start time and end time of each treatment session will be recorded in the case report forms.

6.5 CONCOMITANT THERAPY

For this protocol, a prescription medication is defined as a medication that can be prescribed only by a properly authorized/licensed clinician. Medications to be reported in the Case Report Form (CRF) are concomitant prescription medications, over-the-counter medications, and supplements.

A review of concomitant medications will be performed at each study visit during the treatment period. Subjects will be asked to state all concomitant medications as well as to deny use of all of the prohibited medications.

Treatment with the following medications that are known to have photosensitizing properties will not be permitted, as they are relatively or absolutely contraindicated with concomitant phototherapy (adapted from Appendix 1 in the Omnilux Treatment Protocols manual), unless discussed with and approved by the investigators:

- Amiodarone
- Azathioprine
- Chlorpromazine
- Gold
- Griseofulvin
- Isotretinoin
- Lithium
- Melatonin
- Methotrexate
- Phenothiazine antipsychotics
- Tetracycline antibiotics (e.g., demecocycline, doxycycline, lymecycline, minocycline, oxytetracycline)
- Quinolone derivative antibiotics

6.5.1 RESCUE MEDICINE

N/A

7 STUDY INTERVENTION DISCONTINUATION AND PARTICIPANT DISCONTINUATION/WITHDRAWAL

7.1 DISCONTINUATION OF STUDY INTERVENTION

Discontinuation from LED-RL phototherapy does not mean discontinuation from the study, and remaining study procedures should be completed as indicated by the study protocol. If a clinically significant finding is identified (including, but not limited to changes from baseline) after enrollment, the investigator or qualified designee will determine if any change in participant management is needed. Any new clinically relevant finding will be reported as an adverse event (AE).

The data to be collected at the time of study intervention discontinuation will include the following:

- Details of any adverse events (e.g., nature, severity, relationship to study intervention, and expectedness) will be documented in the CRFs
- Digital photography of the affected site(s), if applicable

Stopping Rules: Adverse events, serious adverse events, and unanticipated problems (as described in *Section 8: Study Assessments and Procedures*) will be monitored and the trial will be halted early if necessary to protect subjects. Any life threatening events and/or deaths (grade 4 and 5 toxicity) attributable to the study protocol will result in halting the study.

7.2 PARTICIPANT DISCONTINUATION/WITHDRAWAL FROM THE STUDY

Participants are free to withdraw from participation in the study at any time upon request, without penalty. For example, the participant may withdraw after receiving the mini-facelift surgery but before starting treatment without being penalized for the procedure-related costs of the mini-facelift surgery.

An investigator may discontinue or withdraw a participant from the study for the following reasons:

- Significant study intervention non-compliance
- Any clinical adverse event (e.g., second-degree or higher skin burning, blistering, swelling, pain, ulceration, change in sensation, muscle weakness, worsening of surgical scar) or other medical condition or situation occurs such that continued participation in the study would not be in the best interest of the participant
- The participant meets an exclusion criterion (either newly developed or not previously recognized) that precludes further study participation
- Unforeseen serious adverse event (e.g., neurological symptoms lasting more than 24 hours) occurs

The reason for participant discontinuation or withdrawal from the study will be recorded on the CRF. Subjects who sign the informed consent form and are randomized but do not receive the study intervention may be replaced. Subjects who sign the informed consent form, and are randomized and receive the study intervention, and subsequently withdraw, or are withdrawn or discontinued from the study, will be replaced only if the enrollment period is still open.

7.3 LOST TO FOLLOW-UP

A participant will be considered lost to follow-up if he or she fails to report to at least one scheduled study visit and is unable to be contacted by the study site staff to complete all protocol-required study procedures.

The following actions must be taken if a participant fails to return to the clinic for a required study visit:

- The site will attempt to contact the participant and reschedule the missed visit within a reasonable time window as determined by the PI (taking into consideration the time-sensitive nature of the treatment regimen and the relative flexibility of timing of the long-term follow-up visits) and counsel the participant on the importance of maintaining the assigned visit schedule and ascertain if the participant wishes to and/or should continue in the study.
- Before a participant is deemed lost to follow-up, the investigator or designee will make every effort to regain contact with the participant (where possible, 3 telephone calls and, if necessary, a certified letter to the participant's last known mailing address or local equivalent methods). These contact attempts should be documented in the participant's medical record or study file.
- Should the participant continue to be unreachable, he or she will be considered to have withdrawn from the study with a primary reason of lost to follow-up.

8 STUDY ASSESSMENTS AND PROCEDURES

8.1 EFFICACY ASSESSMENTS

Refer to *Section 1.3: Schedule of Activities,* for the specific timing of procedures and evaluations to be done at each study visit. All procedures and evaluations will be performed by qualified personnel.

Study Specific Procedures and Evaluations for Efficacy

- Digital photographs of the treatment sites will be taken immediately before and after each treatment session, as well as at each follow-up visit, to track the appearance of the incisions/scars for outcome measures. During the analysis phase, the standardized photographs will be rated in a blinded fashion by an independent panel of expert dermatologists using a visual analogue scale (VAS).
 - The VAS is a validated photograph-based scale that is presented as a 10 cm horizontal line, with the extreme ends of 0 indicating normal skin and 10 corresponding to the worst possible scar. Duncan et al. demonstrated that a VAS with scar ranking is a consistent, reliable, and valid method for linear scar assessment.⁶² Micomonaco et al. further developed a VAS-based instrument that incorporates the dimensions of pigmentation, vascularity, observer comfort, contour, and overall severity for the assessment of area scars.⁶³
- Objective scar characteristics will be recorded at follow-up visits using the following tools:
 - ElastiMeter and SkinFibroMeter (Delfin Technologies, Kuopio, Findland) are two noninvasive instruments used to measure skin elasticity and induration, respectively, using the same indentation principle. They each have an indenter, reference plate,

and built-in force sensors. The probe is pressed against the skin surface while the indenter imposes a constant deformation, instantly measuring the skin's elasticity.

- VivoSight (Michelson Diagnostics, Maidstone, UK) is a high-resolution imaging technology based on multi-beam OCT that produces two-dimensional, cross-sectional, real-time imaging of the skin and provides objective measurements of tissue microstructure, including scar depth and collagen density. The scanning procedure is quick and non-invasive.
- Dermo (Connected Physics, Orsay, France) is a novel spectroscopy probe that instantly measures both collagen and water concentration in the dermis.
- Antera 3D (Miravex, Dublin, Ireland) is a novel skin imaging analysis device that uses reflectance mapping of different wavelengths to acquire three-dimensional images of the skin surface and objectively measures multiple skin dimensions. It accurately measures wrinkles, texture, scars, skin color, redness, and pigmentation. The software also compares images to enable progress tracking and assess therapeutic efficacy. ^{67,68}
 - Alternatively, the Cherry3 camera (Cherry Imaging, Yokneam, Israel) is a new stereoscopic optical and high-resolution 3D imaging system that is specifically designed to objectively measure changes in above-surface scar volume after various interventions. It has been shown to be valid, accurate, and practical for assessing scar volume and for monitoring treatment response.⁶⁹
- Skin specimens will be obtained via optional 2 mm punch biopsy on POD 0 (prior to surgery) and POD 30 (first follow-up visit after completion of LED-RL treatment). All optional skin biopsies will be perform by [name] or [name]. Skin specimens will be used for histological analysis and molecular studies.
 - After skin biopsy, the sample will be placed in fixative (10% neutral buffered formalin) for routine tissue processing and embedding. Paraffin embedded sections will be mounted on glass slides and stained with hematoxylin and eosin (H&E) and either Masson's trichrome or picrosirius red for evaluation of collagen. Histological examination of skin specimens will be conducted to quantify the number of Ki-67 positive fibroblasts and to qualify collagen content.⁷⁷
 - High-throughput assays will be performed using subject biopsy specimens to screen for molecular effects associated with LED-RL treatment. Molecular testing will include RNA-Seq, microRNA arrays, and quantitative real-time PCR (RT-PCR).
- Subjective scar evaluations using the Patient and Observer Scar Assessment Scale (POSAS) will be performed by the same blinded investigator (the treating surgeon) in conjunction with the subject at follow-up visits on POD 30, 90, and 180.
 - The POSAS was designed for a subjective evaluation of various types of scars. Van de Kar et al. critically tested the POSAS on linear scars and found it to have good internal consistency, reliability, and agreement.⁵⁸ Each subscale of the POSAS consists of six items rated on a numerical 10-point scale, with 10 indicating the "worst imaginable scar". The observer rates scar vascularity, pigmentation, thickness, relief, pliability, and surface area while the patient assesses pain, itching, color, stiffness, thickness, and relief. The scores of each of the six items are summed for a total score (range 6 to 60).

8.2 SAFETY AND OTHER ASSESSMENTS

Refer to *Section 1.3: Schedule of Activities*, for the sequence of events that should occur during the screening process.

Study Specific Procedures and Evaluations for Safety or Other Purposes

- The subject's medical history will be obtained by interview at the screening visit to screen for exclusion criteria.
- The subject's concomitant medication list will be reviewed at each study visit to screen for prohibited medications.
- A screening photosensitivity test will be conducted prior to enrollment, wherein the potential subject will be exposed to LED-RL for 20 minutes on the non-dominant upper forearm (as recommended by the manufacturer in the Omnilux new-U user guide), and then evaluated 24 hours later for evidence of photosensitivity. Criteria for photosensitivity include, but are not limited to: warmth, erythema, edema, blistering, rash, pain, or discomfort lasting more than 24 hours. If no adverse events occurred, the potential subject is deemed "non-photosensitive" and thus eligible for participation in the study.
- At the screening visit, the mini-facelift surgery will be discussed with the subject, including details of the procedure, risks, benefits, alternative options, expected outcomes, and pre- and post-operative instructions.
- The mini-facelift surgery will be performed in-office under local anesthesia by [name] (co-investigator and board-certified dermatologic surgeon).
- A targeted physical examination of the treatment sites (i.e., the periauricular skin and surrounding areas) will be performed at each study visit.
- Each treatment session will be monitored for any safety issues or adverse events, either reported by the subject or observed by the investigator.
- Subjects will be provided with a daily diary to record any adverse events experienced at home during the 3-week treatment period. Investigators will call subjects on a weekly basis to monitor for adverse events during the same time period.
 - Common expected post-treatment effects of transient (i.e., lasts less than 24 hours) erythema, warmth, or edema at the treated sites will be recorded. However, any occurrence of these expected effects will not be considered an adverse event in safety data reports, unless the effect lasts more than 24 hours or is considered serious.
- An exit questionnaire will be administered at the final study visit to assess for patient-reported outcomes and elicit other feedback.

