	 vitro data (160 J/cm² to 480 J/cm²), we will conduct a dose-ranging, randomized, parallel group, split-face, single-blind, mock-controlled Phase II study to evaluate the efficacy of LED-RL phototherapy in preventing or limiting skin fibrosis in a mini-facelift surgical wound model. Primary Objective: To evaluate the clinical efficacy of LED-RL phototherapy in the prevention of skin fibrosis in subjects undergoing elective mini-facelift surgery Secondary Objectives: To evaluate the histological, ultrastructural, and molecular changes that occur in vivo as a result of LED-RL phototherapy To detect clinically meaningful changes in scar characteristics after LED-RL phototherapy To continue to assess the safety of LED-RL phototherapy on human skin
Endpoints:	 Primary Outcome Measure: Difference in quantitative scar pliability between the treated and control incision sites Secondary Outcome Measures: Difference in objective measurements of key scar characteristics (collagen and water concentration, wrinkles, texture, diameter, area, volume of elevation, pores, pigmentation, vascularity) between the treated and control incision sites Difference in the Patient and Observer Scar Assessment Scale (POSAS) scores between the treated and control incision sites Difference in the photograph-based Visual Analogue Scale (VAS) scores between the treated and control incision sites Histological and molecular analyses of treated and control skin specimens Incidence of adverse events
Study Population:	A total of 30 subjects will be enrolled. Individuals of any sex, race/ethnicity, and age who are suitable candidates for mini-facelift surgery and who do not meet exclusion criteria will be eligible for this study.
Phase:	2
Description of Sites/Facilities Enrolling Participants:	Subjects will be enrolled at a single site, SUNY Downstate Medical Center. The study is not intended to include sites outside of the US.

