6 STUDY INTERVENTION

6.1 STUDY INTERVENTION(S) ADMINISTRATION

6.1.1 STUDY INTERVENTION DESCRIPTION

The LED light source is the Omnilux new-U handheld LED phototherapy device, which is commercially available and FDA-cleared for the treatment of periorbital wrinkles. This device has not been approved or cleared for the indications the protocol is designed to investigate (skin fibrosis). The device has a 3-position switch that allows the user to select the red light output (switch down).

The mock therapy device emits no irradiation. The mock therapy device has a ventilation fan and functional resistors designed to sound, look, and feel (i.e., temperature matched) similar to the phototherapy treatment device, but does not emit LED-RL.

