8.3 ADVERSE EVENTS AND SERIOUS ADVERSE EVENTS

8.3.1 DEFINITION OF ADVERSE EVENTS (AE)

Adverse event means any untoward medical occurrence associated with the use of an intervention in humans, whether or not considered intervention-related (21 CFR 312.32 (a)).

In this study, there are predefined "common expected post-treatment effects" that should be transient (i.e., lasts less than 24 hours): erythema, warmth, and edema at the treated sites. These effects will be recorded on CRFs on safety monitoring, but will not be considered AEs unless the effect

persists longer than expected (i.e., does not resolve within 24 hours of treatment administration) or meets the definition of a serious AE.

Close attention will be paid to any incidences of cutaneous blistering at the treated sites, either within the incision sites or on the peri-incisional skin.

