8.3.5 ADVERSE EVENT REPORTING

All required reportable events must be reported to the IRB within the deadlines specified in the SUNY Downstate Medical Center Policy IRB-01: Human Research Protections Program. Unanticipated adverse device effects (UADEs) will be reported as soon as possible, but no later than 10 days.

Any AEs that occur in-office during or immediately after treatment sessions, or reported by the subject in the AE diary or in weekly phone calls, will be captured on the appropriate CRF. Information to be collected includes a description of the AE, time of onset, severity, relationship to the study intervention, and time of resolution/stabilization.

Subjects will be counseled regarding the expected outcome of skin erythema and warmth, found to resolve within 24 hours in other clinical studies and occurs in 10% of participants.^{70,71} For this study, the common expected post-treatment side effects of transient erythema, warmth, and swelling at the treated sites will be recorded, but will not be considered an AE for the purposes of safety reports.

All AEs will be reported to the designated medical monitor ([name]), independent safety monitor ([name]), and internal faculty committee at monthly meetings. Please refer to *Section 10.1.6: Safety Oversight* for the composition of the internal committee. [name] is the Director of Clinical Trials & Research in the Department of Dermatology at SUNY Downstate whose responsibilities include: managing and ensuring research compliance; monitoring all departmental clinical trials for AEs; and overseeing appropriate reporting of AEs to the IRB. AEs will be reported to the IRB, NIH, and FDA on a quarterly basis. The PI is responsible for completing and signing off on the AE reports.

[figure not shown]

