9.2 SAMPLE SIZE DETERMINATION

The study will have three treatment arms (LED-RL 160 J/cm², LED-RL 320 J/cm², and LED-RL 480 J/cm²) with 10 subjects each. The primary outcome measure is the difference in pliability between a treated incision site and the contralateral mock-treated incision site.

To calculate the sample size for this study, we anticipate that the minimal clinically important difference in scar pliability is 15%, based on minimum decrease in fibroblast cell number after LED-RL treatment from our *in vitro* data. A power analysis plan predicted that with 9 subjects, the study would have greater than 80% power to detect a 15% difference in pliability by using a two-sided paired *t*-test. To take into account a dropout rate of 10%, 10 subjects will be enrolled in each treatment arm. Up to 150 potential participants will be screened and a total of 30 subjects will be enrolled in the study.

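### The exemption of transient redness, warmth and swelling from adverse-event status does not say whether it covers the mock side, and the planned safety table does not separate the two sides of the face

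*Combined protocol and SAP*

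**What the plan says.** The exemption is stated three times, each time for the same undefined sites.

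- Section 8.2: transient "erythema, warmth, or edema at the treated sites will be recorded. However, any occurrence of these expected effects will not be considered" adverse events in safety reports, unless the effect lasts more than 24 hours or is serious.
- Section 8.3.1: the predefined expected effects are "erythema, warmth, and edema at the treated sites", with the same two exceptions.
- Section 8.3.5: "transient erythema, warmth, and swelling at the treated sites will be recorded, but will not be considered an AE" for safety reports.

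None of the three mentions the mock or control side. Anything outside the exemption falls under the general definition in Section 8.3.1, which covers "any untoward medical occurrence associated with the use of an intervention in humans, whether or not considered intervention-related".

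Section 9.4.4 plans to summarise the number of subjects with adverse events in each treatment group, with a breakdown by event type. It gives no split by side of face and no table of the expected effects, although Section 3 makes the incidence of expected effects part of the safety profile.

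**The concern.** Each subject has one LED-RL side and one mock side, handled in the same session for the same time. That design could show whether a short-lived reaction comes from the light or from heat, contact, cleaning or a healing incision. It can do so only if both sides are classified by one rule and reported separately.

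If the treated sites are the LED-RL sites only, a few hours of redness is an expected effect on one side of the face and an adverse event on the other. A reaction on the mock side is plausible. Section 6.1.1 describes the mock device as having "functional resistors designed to sound, look, and feel (i.e., temperature matched) similar to the" active device, and Section 6.1.2 has it held within 1 cm of alcohol-cleaned skin for 30, 60 or 90 minutes. The research coordinator who observes the sessions and assesses safety (Section 6.1.2) knows the randomization codes (Section 6.3), so a side-dependent rule could be applied in practice.

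At stake are the adverse-event counts sent to the safety monitors, the IRB, NIH and FDA under Section 8.3.5 and summarised under Section 9.4.4, and the study's stated objective of continuing to assess LED-RL safety.

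**Working it through.** The documents give no figure to reproduce on this point. The check is a comparison of wording, followed by arithmetic for scale.

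**1. What treated means elsewhere**

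| Points to the LED-RL side only | Points to both sides |
|---|---|
| Section 1.1 compares endpoints "between the treated and control incision sites" | Section 2.1 calls the periauricular incisions, without distinction, the treatment sites |
| Section 4.1 says the untreated side gets mock therapy | Section 8.2 itself uses treatment sites for the periauricular skin to be examined |
| Section 9.2 contrasts "a treated incision site and the contralateral mock-treated incision site" | Section 9.1 calls the control incision mock-treated |
| Section 9.4.2 has a model factor for whether treated, and Section 10.2 separates treated from untreated incisions | Section 6.1.2 lists the expected effects with no limit to one side |

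Most contrasts support the narrow meaning. Where the control side is called treated, it carries the prefix mock. Section 2.3.1 also lists these effects among the risks of LED-RL and anticipates no physical risk from mock irradiation. The wide meaning remains possible, since the term is not defined.

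**2. Consequence of each reading**

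- Narrow: a transient mock-side reaction is outside the exemption. The general definition in Section 8.3.1 applies whether or not the event is related, so the reaction can be an adverse event. The same reaction on the LED-RL side is not.
- Wide: both sides are exempt, but the text does not say so, and staff may classify identical reactions differently.

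**3. Where the events would go**

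Section 9.4.4 counts subjects by dose group. A subject whose only event is on the mock side adds one to that dose group's count, where it cannot be told apart from an LED-RL event.

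**4. Scale under the narrow reading**

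Inputs: 30 subjects, 10 per arm (Section 9.2). The share p of subjects with a transient mock-side reaction is assumed, because the documents give none.

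Expected subjects = 30 × p. Chance of at least one among n subjects = 1 − (1 − p)^n.

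| Assumed p | Expected of 30 | At least one of 30 | At least one in an arm of 10 |
|---|---|---|---|
| 2% | 0.6 | 1 − 0.98^30 = 45% | 1 − 0.98^10 = 18% |
| 5% | 1.5 | 1 − 0.95^30 = 79% | 1 − 0.95^10 = 40% |
| 10% | 3 | 1 − 0.90^30 = 96% | 1 − 0.90^10 = 65% |

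The 10% row borrows the participant rate that Section 8.3.5 cites for erythema and warmth in other clinical studies. It is not a mock-device rate.

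**The case against.** The strongest reply is that this is an ambiguity of wording with little consequence. No section says that a transient mock-side reaction is an adverse event, and several use treatment sites for both sides. Phase I saw no adverse events with the mock device (Section 2.3.1). Sessions are observed, the skin is examined at each visit, and photographs are taken before and after each session, so a mock-side reaction would hardly go unnoticed. The case report forms are not among the documents and may already have a field for side. No efficacy result, serious-event rule or stopping rule is touched.

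Most of this stands, and it limits the point to a clarification. It does not remove it. The Phase I experience was on normal skin, and Section 3 says that safety in this wound model may differ. Observation and photography do not settle how a reaction is classified or in which column it is reported.

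A reader might also infer that the rule biases the safety comparison in favour of LED-RL. The documents do not support that. No within-face adverse-event comparison is planned, and in the table that is planned a mock-side event raises the count of an LED-RL dose group, which makes the intervention look worse. A reader might likewise expect a spurious dose trend, since mock contact time rises with dose group. That would need a mock-side rate that rises with contact time, for which there are no data, and Section 9.4.4 plans no trend test.

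**Conclusion.** The point holds as a gap in definition and reporting. All three statements of the exemption leave the mock side unaddressed, and the more natural reading of the term permits different classification of identical reactions on the two sides. The planned table then pools the sides, so it cannot separate effects of the light from effects of heat, contact or wound healing, although every subject has a mock control side.

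The stronger statement, that the plan definitely counts the reaction on one side and not on the other, goes too far because the term is undefined. The size is unknown. The expected 0.6 to 3 subjects of 30 rest on the narrow reading and on assumed mock-side rates of 2% to 10%. The change is worth making under either reading because it costs little and lets the split-face design serve the safety objective.

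**What to change.** - In Sections 8.2, 8.3.1 and 8.3.5, replace the reference to the treated sites with *at the LED-RL site or the mock site*, so that the existing 24-hour rule applies unchanged to both sides.
- Record the expected effects by side at each treatment session.
- In Section 9.4.4, tabulate adverse events and expected effects by side (LED-RL versus mock) within dose group, as descriptive counts.

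The cost is a side field on the case report form, if it does not already have one, and one more descriptive table. No added visits are needed.

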Physical risks of the proposed LED-RL phototherapy include potential toxicity and lack of efficacy. There is low risk of infection as we will not treat non-intact skin (since presence of open wound(s) at the treatment site is an exclusion criterion) and all LED-RL phototherapy devices will be cleaned with disinfectant before and after each treatment session. Common expected post-treatment effects include mild erythema (redness), warmth, and swelling that is transient (i.e., lasts less than 24 hours). Subjects may have tenderness or swelling at the treatment site. Since darker skin pigment absorbs more light energy in the epidermis, it is possible that subjects with darker skin types may experience a greater sensation of epidermal warmth, textural changes, or dyspigmentation. Due to the split-face study design (i.e., only one surgical incision receives LED-RL phototherapy), there is a possibility of uneven cosmetic results of the scar appearances at the conclusion of the study. That is, the scar on one side of the face may look better, worse, or the same as the scar on the other side.

Potential serious adverse events including, but not limited to, second-degree or higher skin burning, blistering, persistent swelling, persistent pain, ulceration, change in sensation, mucle weakness, or worsening of surgical scar will be monitored and the trial will be halted early if necessary. While we have tested the effects of LED-RL on fibroblasts, it is not known whether LED-RL alters the function of other cell types *in vivo*. At the doses studied, there may be inhibitory effects on other cells found in the epidermis and dermis such as keratinocytes, melanocytes, endothelial cells, neurons and immune cells. Due to the location of LED-RL phototherapy on the face, there is a theoretical risk of neurological side effects such as headaches, malaise, fatigue, and change in hearing.

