To continue to assess	The safety profile is determined by the	While two phase I studies demonstrated
the safety of LED-RL	incidence of common expected post-treatment	the safety of LED-RL in healthy subjects, the
, phototherapy on	effects, adverse events, serious adverse events,	safety of LED-RL in a mini-facelift surgical
human skin	and unanticipated problems throughout the	wound model may differ from the safety on
	study. Special attention will be paid to the	normal human skin. In addition, differential
	identification of any differential safety findings	safety effects of LED-RL on different skin
	based upon skin type (i.e., race and ethnicity),	types have not been described previously,
	given the findings of our previous Phase I trials.	but our previous research suggest that
		darker skin types may be more
		photosensitive to LED-RL.

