9.4.4 SAFETY ANALYSES

AEs, SAEs, and UPs will be recorded and reported as described in the protocol. The information documented about each event or problem includes onset, duration, severity, relationship to the study intervention, and outcome. Summary statistics of safety data will be presented as number of subjects who experienced AEs in each treatment group and a breakdown of the event types. AEs will be coded according to the terminology in the Medical Dictionary for Regulatory Activities (MeDRA). AEs leading to premature discontinuation from the study and serious treatment-emergent AEs will also be presented.

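### Section 3 puts the incidence of expected post-treatment effects in the safety endpoint, but no planned summary reports that incidence

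*Combined protocol and SAP*

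**What the plan says.** - **Endpoint.** The safety row of Section 3 bases the safety profile on the "incidence of common expected post-treatment" effects, together with AEs, SAEs and UPs. It also promises particular attention to differences by skin type. The synopsis (1.1) is narrower and lists only "Incidence of adverse events".
- **Classification.** Section 8.2 records transient erythema, warmth and edema, but "any occurrence of these expected effects will not be considered an adverse event in safety data reports", with the exception "unless the effect lasts more than 24 hours or is considered serious". Section 8.3.1 agrees: "These effects will be recorded on CRFs on safety monitoring, but will not be considered AEs unless the effect" outlasts 24 hours or is serious. Section 8.3.5 repeats the rule for transient effects without restating the seriousness exception.
- **Analysis.** Section 9.4.4 opens with "AEs, SAEs, and UPs will be recorded and reported as described in the protocol". It then plans the number of subjects with AEs per treatment group, a breakdown by event type, AEs leading to discontinuation, and serious treatment-emergent AEs. Expected effects are not named.
- **Descriptors.** Section 2.3.1 says "Common expected post-treatment effects include mild erythema (redness), warmth, and swelling that is transient". Sections 2.3.3 and 6.1.2 also call the erythema mild. Sections 8.2, 8.3.1 and 8.3.5 do not use that word.

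**The concern.** The plan defines an endpoint component, collects it, and then gives it no place in the safety analysis. On the protocol's own account, these are the common reactions to the light. With 10 subjects per arm they may be the only reactions frequent enough to show a gradient by dose or skin type.

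The documents give reasons to want that information. Section 4.2 warns that fluences safe on normal skin may cause problems in post-surgical skin. Section 4.3 hypothesises that skin of color is more photosensitive. Yet 9.4.4 has no split by skin type or by LED versus mock side, and the subgroup analysis in 9.4.7 concerns pliability only.

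The protocol also shows how an AE-only description can hide such effects. Section 4.1 cites two published studies of a handheld LED device as free of adverse events. Section 8.3.5 cites the same two for erythema and warmth in 10% of participants.

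**Working it through.** The plan states no figure to reproduce here. The check is whether endpoint, classification and analysis connect, followed by arithmetic for scale.

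**Step 1: look for a summary of expected effects in each analysis section.**
- 9.4.4 (safety): AEs, SAEs and UPs only. A transient, non-serious expected effect is not an AE under 8.2 and 8.3.1, and it is not an SAE. It enters only if it is declared part of a UP.
- 9.4.3 (secondary outcomes): tabulated by whether treated, group and time, but as medians and ranges. These do not give the proportion of subjects or sessions affected.
- 9.4.8: individual listings, with no summary.
- 9.4.9 (exploratory): not applicable.

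No section plans an incidence.

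**Step 2: bound on what the AE count could miss.** Inputs: 10 subjects per arm (9.2) and 3 sessions a week for 3 weeks (1.3).
- Sessions per subject: 3 × 3 = 9.
- LED-side subject-sessions per arm: 10 × 9 = 90. In the trial: 30 × 9 = 270.
- Suppose every subject in an arm reacts at every session, always for under 24 hours and never seriously, and no UP is declared. The AE count is then 0/10, with exact two-sided 95% upper limit 1 − 0.025^(1/10) = 30.8%.
- Counted as Section 3 defines the endpoint, the same arm shows 10/10, with exact two-sided 95% lower limit 0.025^(1/10) = 69.2%.

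**Step 3: scale at the only rate the documents give.** Section 8.3.5 says skin erythema and warmth were "found to resolve within 24 hours in other clinical studies and occurs in 10% of participants". Applying 10% to every arm is an assumption. The figure comes from other studies and does not cover swelling. Section 4.1 bases the lowest dose on the maximum doses in those studies, so the figure says little about the arms at 320/160 = 2 and 480/160 = 3 times that dose.
- Expected subjects affected: 10 × 0.10 = 1 per arm; 30 × 0.10 = 3 overall.
- Chance of at least one: 1 − 0.9^10 = 65.1% per arm; 1 − 0.9^30 = 95.8% overall.

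So even at 10%, the trial would very probably produce expected effects. If transient and non-serious, none would enter the 9.4.4 AE count.

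**The case against.** The strongest reply is that nothing is hidden. The 8.2 rule governs what is called an AE; it does not forbid reporting the effects. They go on the CRF (8.3.1), expected reactions are entered in the database (10.1.9.1), and individual data are listed (9.4.8). Keeping expected, transient effects out of the AE count is a legitimate choice. All of this stands. A reader might infer that the effects are barred from safety reports or can never be analysed, and the documents do not say that. What remains is that no incidence is planned.

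A reader might also infer that an intense reaction fading within 24 hours can never be an AE, because the operative sections omit the word mild. The documents do not settle this:
- 2.3.1, 2.3.3 and 6.1.2 describe the expected erythema as mild.
- The seriousness exception still applies, and 8.3.2 includes important medical events by judgment.
- 8.3.3.2 has doubtful observations reported.
- 7.1 treats any new clinically relevant finding as an AE.

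This is an ambiguity to reconcile.

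Finally, universal reactions could be declared a UP under 8.4.1, which covers outcomes unexpected in frequency, and 9.4.4 does report UPs. That is a fair limit on the extreme case, but it depends on a judgment that the frequency is unexpected and suggests greater risk. It does not supply the incidence.

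**Conclusion.** The mismatch is real and should be corrected. Followed as written, the plan omits from its safety summary a component that Section 3 places in the safety endpoint. The consequence is limited to the descriptive safety result; the primary analysis and the capture of AEs are untouched.

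The bound is 90 subject-sessions with reactions in one arm against an AE count of zero. It requires every effect to last under 24 hours, none to be serious, and no UP to be declared. It shows what the rules permit and is not a forecast. The 10% calculation (about 1 subject per arm, 3 in 30) rests on carrying an outside rate for erythema and warmth across all three doses and onto healing incisions.

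**What to change.** 1. Add to 9.4.4 a descriptive table, beside the AE table, of expected post-treatment effects. Show subjects affected and sessions affected, by dose group and skin type and by LED versus mock side, with severity and duration where the CRF captures them. No tests are needed, and the AE definition need not change.
2. Confirm that the CRF records both sides. Sections 8.2, 8.3.1 and 8.3.5 speak of the treated sites, and severity and resolution time are specified for AEs but not for these effects. Read the LED-versus-mock comparison of warmth with caution, because 6.1.1 says the mock device is temperature matched.
3. Reconcile the synopsis safety outcome with Section 3.
4. Reconcile 2.3.1, 2.3.3 and 6.1.2, which describe the erythema as mild, with 8.2, 8.3.1 and 8.3.5, which do not. State the seriousness exception consistently across the three Section 8 passages.

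The cost is one extra table, some wording alignment and possibly a small CRF field change. The safety summary will look less favourable than an AE table alone.
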